### **6.3.7 Hy's Law**

Cases where a subject shows elevations in liver biochemistry may require further evaluation, and occurrences of AST or ALT  $\geq 3xULN$  together with total bilirubin  $\geq 2xULN$  may need to be reported as SAEs. Please refer to Appendix E for further instruction on cases of increases in liver biochemistry and evaluation of Hy's Law.

### **6.3.8 Disease progression**

#### **Symptoms of the disease under study**

Asthma symptoms or signs, such as wheeze, cough, chest tightness, dyspnoea, breathlessness and phlegm, will be recorded as AEs when:

- the sign or symptom is serious according to definitions, see Section 6.2,
- the subject discontinues the study due to the sign or symptom, and/or
- the sign or symptom is new to the subject or not consistent with the subject's pre-existing asthma history (defined as within 1 year of Visit 1 as judged by the investigator).

Asthma exacerbations should not be recorded as AEs after randomization, unless it fulfils any of the above criteria. All asthma exacerbations should be recorded in the exacerbation eCRF as per section 5.1.1.

If a subject discontinues IP due to a study specific discontinuation criterion, this should always be recorded as 'Development of study specific withdrawal' on the termination form in the eCRF. In addition, the investigator must assess whether the asthma deterioration should also be reported as an AE leading to discontinuation of IP (DAE)/AE leading to withdrawal from study on the AE form.

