## LIST OF ABBREVIATIONS AND DEFINITION OF TERMS

The following abbreviations and special terms are used in this study Clinical Study Protocol.

| Abbreviation or special term | Explanation   |
|-------------------------------------|--|
| ACQ-6                               | Asthma Control Questionnaire 6   |
| ADA                                 | Anti-Drug Antibodies   |
| AE                                  | Adverse Event  |
| AAER                                | Annual Asthma Exacerbation Rate  |
| AERR                                | Asthma Exacerbation Reduction Rate                                       |
| ALP                                 | Alkaline Phosphatase   |
| ALT                                 | Alanine Aminotransferase   |
| APFS                                | Accessorized Prefilled Syringe   |
| AQLQ(S)+12                          | Standardised Asthma Quality of Life Questionnaire for 12 Years and Older |
| AST                                 | Aspartate Aminotransferase   |
| ATC                                 | Anatomical Therapeutic Chemical  |
| ATS/ERS                             | American Thoracic Society/European Respiratory Society                   |
| BD                                  | Bronchodilator   |
| β-HCG                               | Beta-Human Chorionic Gonadotropin  |
| BUN                                 | Blood Urea Nitrogen  |
| CGIC                                | Clinical-Global Impression of Change                                     |
| CO 2                     | Carbon Dioxide   |
| COPD                                | Chronic Obstructive Pulmonary Disease                                    |
| CSA                                 | Clinical Study Agreement   |
| CSR                                 | Clinical Study Report  |
| DAE                                 | Discontinuation of Investigational Product due to Adverse Event          |
| dECG                                | Digital Electrocardiogram  |
| DNA                                 | Deoxyribonucleic Acid  |
| DPP4                                | Dipeptidyl Peptidase-4   |
| DSMB                                | Data and Safety Monitoring Board   |

| Abbreviation or special term | Explanation   |
|-------------------------------------|--|
| EC                                  | Ethics Committee, synonymous to Institutional Review Board (IRB) and Independent Ethics Committee (IEC)  |

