Discontinuation of IP does not necessarily mean discontinuation of follow-up or termination of study participation. Compliant subjects who are discontinued from the IP should be encouraged to continue to undergo all study related visits/procedures for the full 52-week study period in order to support the final efficacy and safety analysis for tralokinumab (see section 8). The reason for premature discontinuation of IP will be documented in the source documentation and recorded in the electronic case report form (eCRF).

It is essential to collect as much data as possible for all subjects throughout the study and especially all potential endpoint events. Complete withdrawal from the study (i.e., withdrawal of consent) has a direct negative impact on the potential validity of all study data and should be avoided wherever possible.

If the subject permanently discontinues IP prior to their completion of the study and wishes to continue with the study assessments, they may choose from 3 different follow-up options, as described in Section 4.2.

For subjects who wish to withdraw from the study completely refer to Section 3.10.

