### **6.3.6 Adverse events based on examinations and tests**

The results from protocol mandated laboratory tests and vital signs will be summarized in the CSR. Deterioration as compared to baseline in protocol-mandated laboratory values and vital signs should therefore only be reported as AEs if they fulfil any of the SAE criteria or are the reason for discontinuation of treatment with the IP.

If deterioration in a laboratory value/vital sign is associated with clinical signs and symptoms, the sign or symptom will be reported as an AE and the associated laboratory result/vital sign will be considered as additional information. Wherever possible the reporting Investigator will use the clinical, rather than the laboratory term (e.g., anaemia versus low haemoglobin value). In the absence of clinical signs or symptoms, clinically relevant deteriorations in non-mandated parameters should be reported as AE(s).

Deterioration of a laboratory value, which is unequivocally due to disease progression, should not be reported as an AE/SAE.

Any new or aggravated clinically relevant abnormal medical finding at a physical examination as compared with the baseline assessment will be reported as an AE.

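### Section 6.3.8 makes familiar, non-serious asthma worsening an AE only if the subject leaves the study, so an IP stop for it with continued follow-up can be absent from the DAE tables

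*Protocol*

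**What the plan says.** Section 6.3.8 (Disease progression) records asthma signs or symptoms as AEs on any of three criteria:

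- seriousness: "the sign or symptom is serious according to definitions, see Section 6.2";
- discontinuation: "the subject discontinues the study due to the sign or symptom, and/or";
- novelty: "the sign or symptom is new to the subject or not consistent with the" subject's earlier asthma history.

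For exacerbations it adds: "Asthma exacerbations should not be recorded as AEs after randomization, unless it fulfils any of the above criteria". Its last paragraph opens "If a subject discontinues IP due to a study specific discontinuation criterion" and, in that situation, obliges the investigator to consider whether the asthma deterioration is also a DAE.

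Other parts of the protocol treat stopping IP and leaving the study as different things. Section 3.9.1 states: "Discontinuation of IP does not necessarily mean discontinuation of follow-up or termination of study participation". Section 4.2 offers three follow-up options after an IP stop. The abbreviation list expands DAE as "Discontinuation of Investigational Product due to Adverse Event". Section 6.3.6 reports deteriorating laboratory values and vital signs as AEs only if they fulfil "any of the SAE criteria or are the reason for discontinuation of treatment with the IP". Section 6.3.3 collects the action taken with IP and withdrawal from the study as two separate AE variables. Section 8.5.8.1 plans DAEs in the overall AE summary and in a table of their own, with a listing of discontinuations due to AEs.

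**The concern.** The discontinuation criterion in 6.3.8 is keyed to the wrong event for a DAE. A DAE is about stopping IP, but familiar asthma worsening re-enters the AE data only through leaving the study. Since the protocol asks subjects who stop IP to stay to Week 52, stopping IP and remaining in follow-up is the intended path, and it is the path on which this criterion is not met.

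The DAE summaries are a main description of tolerability. If they depend on whether a subject also left the study, two subjects who stop IP for the same event are counted differently, and the better retention works, the fewer such stops are counted. Asthma is the disease under treatment, so stops for asthma worsening could differ between arms, in a direction that cannot be foreseen from the protocol.

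**Working it through.** No figure is involved. The check follows one event through the rules: non-serious asthma worsening leads to an IP stop, and the subject stays in follow-up.

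1. **Starting point.** Section 6.1 counts deterioration of a pre-existing condition as an AE. Section 6.3.8 is therefore an exception that takes asthma out, and its three criteria decide what comes back in.

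2. **Worsening that is new or out of keeping with the asthma history.** The third criterion is met whether or not the subject leaves. The event is an AE and can be a DAE. No gap.

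3. **IP stopped for a study-specific criterion.** The last paragraph of 6.3.8 requires a DAE assessment. The asthma-specific item named under point 7 of the list in 3.9.1 is an event requiring intubation, which would normally already be serious. No gap, but the paragraph adds little.

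4. **Familiar worsening, IP stopped by subject decision or because of judged risk (points 1 and 3 in 3.9.1).** Not serious, so the first criterion fails. The subject stays, so the second fails. Not new or atypical, so the third fails. The last paragraph is not triggered. Section 6.3.8 gives no AE route, so no DAE follows from it.

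5. **Familiar worsening, IP stopped under point 2 in 3.9.1 (an AE that contraindicates dosing).** The stop reason presupposes an AE. If the event is an exacerbation, 6.3.8 says it should not be recorded as one. The two sections conflict.

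6. **Same event as in step 4, but the subject also leaves the study because of it.** The second criterion is met and the event is an AE, so it can enter the DAE table.

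The gap lies in steps 4 and 5. Comparing steps 4 and 6, the only thing that changes the count is departure from the study, which is not part of the DAE definition.

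**Size.** The number affected would be 770 × p × r, where p is the proportion stopping IP for familiar, non-serious worsening outside the study-specific criteria and without another AE route, and r is the proportion of those who stay in follow-up. The protocol states neither p nor r, nor how they might differ by arm, so no count is given.

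**The case against.** The strongest case on the other side has five parts.

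- **Other routes exist.** Section 6.3.6, with 5.1.7, makes a new or aggravated clinically relevant examination finding an AE. Worse wheeze at the IP discontinuation visit could qualify, and nothing says 6.3.8 overrides this. That stands, and it narrows the gap to subjects without such a finding. Point 2 in 3.9.1 narrows it less, because for exacerbations it relies on an AE that 6.3.8 keeps off the AE form.
- **The DAE paragraph shows intent.** The list of study-specific criteria is introduced as inclusive, and a duty to assess DAEs would be nearly empty if confined to intubation. This suggests that the authors wanted asthma-driven IP stops assessed. The text still limits the duty to study-specific criteria, so the intent supports correcting the wording.
- **There is no outright ban.** For signs and symptoms, 6.3.8 says when they will be recorded and does not forbid anything else. For exacerbations it says only that they should not be recorded. A site could therefore record more than 6.3.8 requires, but different sites would then do different things.
- **The events are not lost.** Exacerbations go to their own eCRF module and count in the primary endpoint even after IP is stopped (5.1.1). The reason for stopping IP is recorded (3.9.1) and tabulated by treatment group (8.5.3). That stands, but it does not make the DAE table agree with its own definition.
- **Keeping disease events out of the AE tables is deliberate, and safety is descriptive.** Both are true. No test or success criterion is affected. But the exclusion is deliberately lifted for discontinuation, and it is lifted on the wrong kind.

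**Conclusion.** The wording of 6.3.8 is wrong as it stands, in a narrow class: non-serious worsening, consistent with the subject's asthma history, leading to an IP stop outside the study-specific criteria, with continued follow-up and no separately reportable aggravated examination finding. Such a stop has no AE route in 6.3.8 and can be absent from the DAE summaries in 8.5.8.1.

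Three stronger readings are tempting and are not supported:

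- A reader might infer that all non-serious worsening needs departure from the study to become an AE. The third criterion in 6.3.8 shows otherwise.
- A reader might infer that these events disappear from the trial's data. The exacerbation module (for protocol-defined exacerbations) and the disposition reasons keep them visible.
- A reader might infer a known bias between arms. The protocol gives no rate and no direction, so only the possibility of a difference can be stated.

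The conclusion assumes that sites follow 6.3.8 as written and that the study-specific criteria are those listed in 3.9.1. It is worth correcting because the inconsistency is plain and cheap to remove.

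**What to change.** Reconcile 6.3.8 with the DAE definition and with 6.3.6. Word the second criterion so that it is met when the subject stops IP or leaves the study because of the sign or symptom, and state that the same test applies to exacerbations. Carry this into the eCRF instructions.

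This edition is dated 09 June 2017 and the study is expected to end by Q3 2017, so new wording alone would reach few events. The effective step is a data query before database lock, made without knowledge of treatment: compare every asthma-related reason for stopping IP with the AE form, and ask the site to resolve cases that have no matching AE.

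The cost is a few words, one query, and slightly more AEs and DAEs reported. Some disease worsening will then appear in both the efficacy and the safety tables. A footnote to the DAE table identifying asthma events would keep that clear.

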## 6.4 Reporting of serious adverse events

All SAEs must be reported, whether or not considered causally related to the IP, or to the study procedure(s). All SAEs will be recorded in the eCRF.

If any SAE occurs during the course of the study, Investigators or other site personnel must inform the appropriate AstraZeneca representatives within one day (i.e., immediately) but **no later than 24 hours** of when he or she becomes aware of it.

The designated AstraZeneca representative will work with the Investigator to ensure that all the necessary information is provided to the AstraZeneca Subject Safety data entry site **within 1 calendar day** of initial receipt for fatal and life threatening events **and within 5 calendar days** of initial receipt for all other SAEs.

For fatal or life-threatening AEs where important or relevant information is missing, active follow-up will be undertaken immediately. Investigators or other site personnel must inform AstraZeneca representatives of any follow-up information on a previously reported SAE within 1 calendar day (i.e., immediately) but no later than 24 hours of when he or she becomes aware of it.

Once the Investigators or other site personnel indicate an AE is serious in the WBDC system, an automated email alert will be sent to the designated AstraZeneca representative(s).

If the WBDC system is not available, then the Investigator or other study site personnel reports a SAE to the appropriate AstraZeneca representative(s) by telephone.

The AstraZeneca representative(s) will advise the Investigator/study site personnel how to proceed.

The reference document for definition of expectedness/listedness is the Investigator's Brochure for the AstraZeneca IP.

## 6.5 Overdose

An overdose with associated AEs is to be recorded as the AE diagnosis/symptoms on the relevant AE modules in the eCRF, as well as in the Overdose eCRF module.

An overdose without associated symptoms is only to be reported on the Overdose eCRF module.

If an overdose with the AstraZeneca study drug occurs during the course of the study, the Investigator, or other site personnel, must inform appropriate AstraZeneca representative(s) immediately, and **no later than 24 hours** of when he or she becomes aware of it.

The designated AstraZeneca representative will work with the Investigator to ensure that all relevant information is provided to the AstraZeneca Subject Safety data entry site.

For overdoses associated with a SAE, the standard reporting timelines apply, see Section 6.4. For other overdoses, reporting must occur within 30 days.

## 6.6 Pregnancy

All pregnancies and outcomes of pregnancy should be reported to AstraZeneca.

### 6.6.1 Maternal exposure

If a subject becomes pregnant during the course of the study IP should be discontinued immediately.

Pregnancy itself is not regarded as an AE unless there is a suspicion that the IP under study may have interfered with the effectiveness of a contraceptive medication. Congenital abnormalities/birth defects and spontaneous miscarriages should be reported and handled as SAEs. Elective abortions without complications should not be handled as AEs. The outcome of all pregnancies (spontaneous miscarriage, elective termination, ectopic pregnancy, normal birth or congenital abnormality) should be followed up and documented even if the subject was discontinued from the study.

If any pregnancy occurs in the course of the study, then the Investigator or other site personnel will inform the appropriate AstraZeneca representatives within 1 day (i.e., immediately) but **no later than 24 hours** of when he or she becomes aware of it.

The designated AstraZeneca representative will work with the Investigator to ensure that all relevant information is provided to the AstraZeneca Subject Safety data entry site within 1 or 5 calendar days for SAEs (see Section 6.4) and within 30 days for all other pregnancies.

The same timelines apply when outcome information is available.

The pregnancy module in the eCRF will be used to report the pregnancy and the pregnancy outcome module will be used to report the outcome of the pregnancy.

### 6.6.2 Paternal exposure

There is no restriction on fathering children or donating sperm during the study.

## 6.7 Management of IP related toxicities

Appropriate drugs, such as epinephrine, H1 and H2 antihistamines, and corticosteroids, as well as medical equipment to treat acute anaphylactic reactions must be immediately available

when IP is being administered. Study site personnel must be trained to recognize and treat anaphylaxis (Lieberman et al 2010). Details on anaphylaxis management are provided in Appendix G.

Anaphylaxis will be defined as serious reaction that is rapid in onset and may cause death (Sampson et al 2006). Anaphylaxis typically manifest as 1 of 3 clinical scenarios:

1. The acute onset of a reaction (minutes to hours) with involvement of the skin, mucosal tissue or both and at least one of the following: a) respiratory compromise; or b) reduced blood pressure or symptoms of end-organ dysfunction
2. Two or more of the following that occur rapidly after exposure: involvement of the skin/mucosal tissue, respiratory compromise, reduced blood pressure or associated symptoms and/or persistent gastrointestinal symptoms
3. Reduced blood pressure after exposure.

Subjects will have had a pre-assessment (i.e., vital signs and lung function) prior to IP administration. At Visits 3 through 6, subjects should be observed for a minimum of 2 hours after IP administration for the appearance of any acute drug reactions. For the remaining visits involving IP administration, subjects will be observed for a minimum of 1 hour after IP administration for any such reaction.

In order to help understand the potential drug-relatedness of any acute reaction, a blood sample should be drawn during the event for additional ADA testing (if not already scheduled as per table 1 for this visit). If an anaphylactic reaction occurs, a blood sample will be drawn from the subject as soon as possible after the event, at 60 minutes  $\pm$  30 minutes after the event, and at discharge for analysis of serum tryptase. The serum tryptase sample will be tested at the local lab or central lab where applicable.

## **6.8 Study governance and oversight**

### **6.8.1 Independent Adjudication Committee**

Tralokinumab is being developed for the treatment of severe asthma. There is considerable variation in the severity of subjects who seek ER or urgent care, and in the clinical thresholds used to determine the need for hospitalization.

An Independent Adjudication Committee, blinded to subject treatment, will evaluate all ER or urgent care visits, hospitalizations and deaths, to determine whether or not related to asthma. The adjudication committee will also review cardiovascular, cerebrovascular and malignant adverse events occurring after randomization. The committee will include specialists in pulmonology, cardiology, neurology and oncology and will operate in accordance with a dedicated Adjudication Committee Charter/Manual of Operations.

## **6.8.2 Data and safety monitoring board**

An external DSMB will monitor and protect the safety of adolescent subjects throughout the double blind treatment period of the study. The DSMB members will be selected for their expertise. The voting members of the DSMB will be comprised of external individuals including the DSMB chair. To minimize the potential introduction of bias, DSMB members will not have direct contact with the study site personnel or subjects.

The DSMB will review safety data on a regular basis as set out in the DSMB charter. The data for review will be outlined in the DSMB charter. The DSMB will have access to individual treatment codes and will be able to merge these with the collected study data while the study is ongoing. For reference, the DSMB will also have access to study data from adults. Subject enrollment will continue during DSMB review of safety data.

The DSMB will operate in accordance with the dedicated DSMB Charter/Manual of Operations and will be agreed to in advance by the DSMB members.

## **7. INVESTIGATIONAL PRODUCT AND OTHER TREATMENTS**

### **7.1 Identity of investigational product(s)**

All investigational products will be manufactured in accordance with GMP.

Tralokinumab and placebo administered in the study will be a clear to opalescent, colourless to yellow solution free from, or practically free, from visible particles. Subjects will be randomized at Visit 3 (Week 0) in a 1:1 ratio to receive tralokinumab 300 mg, or placebo, Q2W (26 doses).

Each subject will receive two SC injections of 150 mg tralokinumab at each dosing interval to receive a total dose of 300 mg, or placebo. The identity details for the IP are found in [Table 7](#).

**Table 7 Identity of investigational product**

| Investigational product | Concentration and Formulation   | Dosage form and strength   | Manufacturer |
|--------------------------------|--|---|---------------------|
| Tralokinumab                   | Formulated at a nominal concentration of 150 mg/mL in 50mM sodium acetate/acetic acid buffer, 85mM sodium chloride, 0.01% (w/v) PS-80 pH 5.5 solution. | 150 mg/mL solution for injection in an accessorized pre-filled syringe, 1.0 mL fill volume. | MedImmune           |
| Placebo                        | Placebo contains the same excipients, in the same concentration only lacking tralokinumab  | Placebo solution for injection in an accessorized pre-filled syringe, 1.0 mL fill volume.   | MedImmune           |

The accessorized prefilled syringe (APFS) is a single use, disposable system that is designed to administer the labelled dose of the system to the subcutaneous space during one injection and automatically provide a safety mechanism to reduce the occurrence of accidental needle sticks during disposal of the system.

The APFS consists of a prefilled syringe sub-assembly (PFS-SA; 1 mL long prefilled syringe barrel with a 1/2 inch 27 gauge thin wall staked in needle, rigid needle shield, plunger stopper) and a safety device.

